## 9.2 Randomization and Stratification

Participants will be randomized with equal probability to the two arms of the study. Stratification may occur by entry ART regimen (3rd agent class).

## 9.3 Primary Endpoint Assessments

The safety (frequency of maintaining HIV-1 RNA <50 copies/mL) and tolerability (frequency of study drug discontinuation due to study-drug related AEs and frequency of study-drug related ≥ Grade 3 lab or clinical events whether or not study drug was discontinued) of bictegravir + tenofovir alafenamide + emtricitabine in HIV-infected TW on female hormone therapy vs continued ART.

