## **5.0 Study Treatment**

### **5.1 Regimens, Administration, and Duration**

Study treatment is open label bictegravir + tenofovir alafenamide + emtricitabine (only bictegravir is investigational).

At entry participants will be randomized 1:1 by the study team to:

ARM A (immediate switch): Switch current ART to bictegravir + tenofovir alafenamide + emtricitabine for 48 weeks

or

ARM B (no switch): Continue current therapy for 48 weeks

If randomized to ARM A at study entry, the subject will substitute bictegravir + tenofovir alafenamide + emtricitabine for their entry ART regimen.

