## **7.0 Toxicity Management**

Criteria for participant management, dose interruptions, modifications, and discontinuation of drug treatment will be mandated only for toxicities attributable to study drug (for Arm A participants). Toxicities due to drugs in the background regimen/entry regimen (for Arm B participants) should be managed according to standard clinical practice, with the goal of maintaining continuous therapy, if possible.

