### **9.6.1 Primary Analysis**

Comparison between treatment arms of the primary endpoint will be undertaken using the Wilcoxon rank-sum test. The primary analysis will be as-treated, excluding participants who do not remain on the study regimen and/or participants who do not have an observed primary endpoint. Participants who discontinue study drug or their background entry regimen for  $\geq 14$  consecutive days will no longer contribute data to the primary outcome after the date on which they first discontinued medication. An intent-to-treat analysis will also be performed as a supplement.

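### The primary as-treated rule in 9.6.1 can remove the very stops and failures that 9.3 counts as endpoint events, and relatedness is not defined for Arm B

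*Combined protocol and SAP*

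**What the plan says.** Section 9.3 gives the primary endpoint two parts: keeping HIV-1 RNA below 50 copies/mL, and tolerability. Tolerability is the "frequency of study drug discontinuation due to study-drug related AEs and frequency of study-drug related" Grade 3 or higher laboratory or clinical events. The latter count even if treatment was stopped, and the comparator is continued ART.

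Section 9.6.1 plans a between-arm test: "Comparison between treatment arms of the primary endpoint will be undertaken using the Wilcoxon rank-sum test". It continues: "The primary analysis will be as-treated, excluding participants who do not remain on the study regimen"; people without an observed primary endpoint are also left out. The next sentence begins "Participants who discontinue study drug or their background entry regimen for" 14 or more "consecutive days will no longer contribute data to the primary outcome after the date on which they first discontinued medication". Last comes "An intent-to-treat analysis will also be performed as a supplement".

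On the meaning of study drug:
- Section 5.1: "Study treatment is open label bictegravir + tenofovir alafenamide + emtricitabine".
- Section 7.0: management criteria "will be mandated only for toxicities attributable to study drug (for Arm A participants"); Arm B toxicities are ascribed to the background or entry regimen.
- Section 10.4 names the switch regimen as the study agent for SAE reporting.
- Section 8.1 nevertheless lists the Arm B stop under permanent study drug discontinuation, and 9.6.2 and 9.6.3 report treatment-related events and treatment discontinuation by arm. Section 9.6.2 counts from the start of study treatment, a date that Arm B lacks under 5.1.

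**The concern.** An analysis set that depends on staying on treatment cannot measure how often people stop treatment. If those who stop for a related adverse event are excluded, that component is empty in both arms. Grade 3 or higher events in the same people leave with them, although 9.3 counts such events irrespective of stopping. Section 8.1 also lists confirmed virologic failure as a reason to stop study drug, so failures can leave the HIV-1 RNA component by the same route.

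The attribution gap is separate. A between-arm comparison of related events needs the same rule in both arms, and the plan supplies none for Arm B. Two analysts could follow the text faithfully and report different primary tolerability results from the same data.

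**Working it through.** **Inputs.** From the documents: 24 per arm (9.1), two-sided 0.05 (9.6), rank-sum test (9.6.1). The documents give no expected rate, power or sample size for the primary endpoint, so all event counts, rates and attribution shares below are assumptions.

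**The plan's own figure.** Section 9.1 claims 90% power for a CAP difference of 56 dB/m, SD 53, with 20 per arm. A two-sample t-test calculation gives 90.2%, and 20 × 1.2 = 24. This reproduces, but concerns CAP; only the 24 per arm is used here.

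**Step 1: the discontinuation component.** If k of 24 Arm A participants stop for a related adverse event, the frequency is k/24 in everyone and 0/(24 − k) after exclusion.

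| k | All 24 | After exclusion |
|---|---|---|
| 1 | 4.2% | 0/23 |
| 2 | 8.3% | 0/22 |
| 3 | 12.5% | 0/21 |
| 4 | 16.7% | 0/20 |

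**Step 2: the HIV-1 RNA component.** If two participants have confirmed failure, stop and are excluded, 22/24 (91.7%) suppressed becomes 22/22 (100%).

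**Step 3: the two sentences of 9.6.1 compared.** Suppose four related Grade 3 or higher events in Arm A, two of them in people who stop, and none in Arm B. For 0/1 data the tie-corrected rank-sum statistic is z² = [(N − 1)/N] × Pearson χ², with χ² = N(ad − bc)² / (product of the four margins).
- Exclusion: 2/22 v 0/24. χ² = 46 × 48² / (22 × 24 × 2 × 44) = 2.281; × 45/46 = 2.231; p = 0.135 (Fisher 0.223). Stops: 0/22 v 0/24.
- Date cut-off, events dated up to the stop: 4/24 v 0/24. χ² = 48 × 96² / (24 × 24 × 4 × 44) = 4.364; × 47/48 = 4.273; p = 0.039 (Fisher 0.109). Stops: 2/24 v 0/24.

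**Step 4: the attribution gap.** Suppose both arms have the same true rate p. If Arm B could score only zero, the rank-sum test reaches p < 0.05 at 4 events in Arm A (3 events give 0.077). The chance of this is 1 − Σ(k = 0 to 3) C(24,k) pᵏ(1 − p)²⁴⁻ᵏ. If relatedness is judged per arm but unevenly, the counts are binomial with rates p × share called related. Chance of p < 0.05 against Arm A:

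| Rule (share called related, A v B) | 3% | 5% | 10% | 20% |
|---|---|---|---|---|
| Arm B always zero, all Arm A events related | 0.5% | 3.0% | 21% | 74% |
| Per arm, 80% v 20% | 0.2% | 1.1% | 7.7% | 28% |
| Per arm, 70% v 30% | 0.1% | 0.6% | 4.2% | 14% |
| Per arm, 60% v 40% | 0.1% | 0.3% | 2.1% | 6.2% |
| All-cause counting | 0.3% | 0.9% | 2.4% | 2.7% |

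Section 2.1 reports no bictegravir discontinuations for adverse events in Phase II, which points to the left-hand columns.

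**The case against.** A reader might infer that Arm B scores zero by definition and that the comparison is therefore rigged against the switch. The documents do not support that. Sections 7.0, 8.1, 9.6.2 and 9.6.3, and the comparator clause of 9.3, make a per-arm meaning at least as natural. On that reading the contrast is defined, and what remains is open-label attribution for a new regimen against a stable one, which follows from the declared design. The 21% and 74% figures need both the zero reading and rates that nothing in the documents supports.

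A reader might also infer that safety events disappear from the report. They do not: the supplementary intent-to-treat analysis, the by-arm summaries in 9.5, 9.6.2 and 9.6.3, and the listed reasons for stopping keep them visible.

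The date sentence can be read as explaining how the as-treated rule operates, in which case the stopping event may still count. That is fair, but the preceding sentence says exclude, and nothing says which governs. The example in step 3 also sits on the threshold: with one Arm B event added, neither rule reaches significance (2/22 v 1/24, p = 0.50; 4/24 v 1/24, p = 0.16). It shows that the rules differ, not that a conclusion would flip in practice.

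Finally, 9.6 calls the analysis exploratory and unadjusted for multiplicity. That limits the weight of any p-value, but does not settle who is counted for the only primary objective, which is safety (1.2).

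**Conclusion.** The point holds, with limited stakes, and should be fixed. The as-treated exclusion empties the discontinuation component by construction, drops Grade 3 or higher events in people who stop, and can remove confirmed virologic failures; this follows from the text and needs no assumed rate. How much is lost depends on how many people stop, which the documents do not predict. The undefined relatedness in Arm B is a real gap but a smaller one: at assumed true rates of 3% to 5% the false-signal chance is at most about 3% even in the most extreme case, and it becomes large only at higher rates with very uneven attribution. What is affected is the primary comparison, not the visibility of events.

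**What to change.** 1. In 9.6.1, make the primary set for tolerability all randomised participants who started their assigned regimen (Arm A from first dose, Arm B from randomisation). Count a stop for an adverse event as an event, and count confirmed virologic failure as failure to maintain HIV-1 RNA below 50 copies/mL. Report non-starters separately by arm: Arm B enters already on its regimen, so putting non-starters in the denominator would dilute essentially Arm A alone. Keep as-treated as the supplement under one stated rule, exclusion or date cut-off.
2. In 9.3, 9.6.2 and 9.6.3, define relatedness against the assigned regimen in both arms, with randomisation as the Arm B start date. Because attribution is open label, report all-cause Grade 3 or higher events and adverse-event-driven stops of the assigned regimen by arm beside it.
3. Record the reason for stopping ART in Arm B as in Arm A. Section 6.5 records ART modifications, but does not clearly require the reason in Arm B.
4. Reconcile the two statements in 6.4, one keeping participants who stop for an adverse event on study and one taking off study those who stop for 14 days or more, so that last follow-up is defined.

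Cost: wording changes, slight rewording of the tolerability endpoint, and perhaps one CRF item. Grade 2 or higher symptoms and the main laboratory values are already recorded (6.5, 6.6). All-cause counts will include unrelated events, and open-label reporting bias remains.

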## 9.4 Secondary Endpoints Assessments

- Total lean and fat mass, appendicular lean and fat mass and trunk fat mass, as measured by DXA
- Bone mineral density, as measured by DXA
- Hepatic steatosis and fibrosis, as measured by FibroScan CAP and LSM
- Total cholesterol, HDL cholesterol, triglycerides, LDL cholesterol (direct), oxidized LDL
- Insulin, glucose, HOMA-IR
- Estimated GFR (CKD-Epi equation)
- AST and ALT
- Inflammatory and metabolic biomarkers

## 9.5 Study Monitoring

This is an open label study. Accrual and a summary of all Grade ≥2 signs and symptoms and all Grade ≥3 laboratory abnormalities will be prepared by the central data management site at the McGovern School of Medicine, and reviewed by the study team monthly. The AE summary will be divided by treatment arms and reviewed regularly by the team, as will baseline characteristics, early treatment discontinuations, and study discontinuations. The data management center at the McGovern School of Medicine will also prepare a quarterly report of all AEs by treatment arm to be reviewed by the team.

Approximately six-nine months after enrollment of the first participant, an interim review of the study will occur. An independent Study Monitoring Committee (SMC) comprised of three HIV investigators not involved in the study will review accrual, AE summaries, off-treatment, and off-study rates broken down by randomized

treatment arm. A SMC may also be convened if a reason is identified by the study team, the data management center, or in consultation with the sponsor.

## **9.6 Analyses**

A descriptive analysis of demographic and clinical characteristics will be generated. Continuous variables will be expressed as mean  $\pm$  SD if normally distributed or median with IQR if not normally distributed. Data will be pooled by arm and stratified by ART 3rd drug class. CAP will be used continuously and categorically, using for the latter the following standardized steatosis cut-offs: Grade 1 238 dB/m, Grade 2 260 dB/m and Grade 3 292 dB/m. DXA data will be used continuously for lean and fat mass measurements, and, for bone mineral density, both continuously and categorically, with the latter using standard cutoffs for osteopenia and osteoporosis. Biomarker levels may be log-transformed, where appropriate. Wilcoxon rank-sum and Pearson  $\chi^2$  tests will compare continuous and categorical variables, respectively, between and within groups. Although the sample size is small, regression modeling will be attempted to assess if any observed differences persist after adjustment for confounding factors. All statistical tests will be 2-sided ( $\alpha=0.05$ ). Analysis will be exploratory without adjusting for multiple testing. [name] and [name] (statistician) will oversee analysis plan development/implementation.

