## **1.0 Study Hypotheses and Objectives**

### **1.1 Hypotheses**

1.1.1 Compared to continued ART, switch to bictegravir + tenofovir alafenamide + emtricitabine will not be associated with an adverse side effect profile and will maintain virologic control in HIV-infected transwomen (TW).

1.1.2 After 48 weeks, switch to bictegravir + tenofovir alafenamide + emtricitabine will be associated with improvements in circulating inflammatory and metabolic biomarker profiles (including mortality-associated biomarkers), bone mineral density, fat and lean mass quantities, hepatic fat and insulin resistance vs continued ART.

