### **1.3 Secondary Objectives**

1.3.1 To compare total, appendicular and trunk fat mass by DXA at 48 weeks between TW who switch to bictegravir + tenofovir alafenamide + emtricitabine compared to TW who remain on current ART.

1.3.2 To compare total and appendicular lean mass by DXA at 48 weeks between TW who switch to bictegravir + tenofovir alafenamide + emtricitabine compared to TW who remain on current ART.

1.3.3 To compare bone mineral density by DXA at 48 weeks between TW who switch to bictegravir + tenofovir alafenamide + emtricitabine compared to TW who remain on current ART.

1.3.4 To compare hepatic fat content, as measured by FibroScan controlled attenuation parameter (CAP) measurement, at 48 weeks between TW who switch to bictegravir + tenofovir alafenamide + emtricitabine compared to TW who remain on current ART.

1.3.5 To compare hepatic fibrosis, as measured by FibroScan liver stiffness measurement (LSM), at 48 weeks between TW who switch to bictegravir + tenofovir alafenamide + emtricitabine compared to TW who remain on current ART.

1.3.6 To compare frequency of insulin resistance, as measured by the homeostatic assessment model of insulin resistance (HOMA-IR), at 48 weeks between TW who switch to bictegravir + tenofovir alafenamide + emtricitabine compared to TW who remain on current ART.

1.3.7 To compare fasting lipid levels at 48 weeks between TW who switch to bictegravir + tenofovir alafenamide + emtricitabine compared to TW who remain on current ART.

1.3.8 To compare estimated GFR (using the CKD-Epi equation) at 48 weeks between TW who switch to bictegravir + tenofovir alafenamide + emtricitabine compared to TW who remain on current ART.

1.3.9 To compare AST and ALT levels at 48 weeks between TW who switch to bictegravir + tenofovir alafenamide + emtricitabine compared to TW who remain on current ART.

1.3.10 To compare differences in circulating inflammatory and metabolic biomarker levels (including mortality associated biomarkers) at 48 weeks between TW who switch to bictegravir + tenofovir alafenamide + emtricitabine compared to TW who remain on current ART.

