## **3.0 Study Design**

Participants will be randomized 1:1 to continue current ART or switch to bictegravir + tenofovir alafenamide + emtricitabine for 48 weeks. Blood collection for inflammatory and metabolic biomarker analysis will be performed at weeks 0, 24 and 48. DXA-quantified bone mineral density and lean and fat mass, and Fibroscan-quantified hepatic fat (CAP) and fibrosis (LSM) will be performed at weeks 0 and 48. DXA and Fibroscan will be performed locally at research rates. Blood will be collected on site and stored for batched inflammatory and metabolic biomarker processing.

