## 6.0 Clinical Evaluations

### 6.1 Schedule of Events

	Screen	Baseline*	Week 4	Week 12	Week 24*	Week 36	Week 48*	Early Discontinuation
Demographics	X							
Hormone therapy questionnaires		X						
Medical and medication history	X							
Targeted physical exam with weight, vital signs		X	X	X	X	X	X	
Complete physical exam and height	X							
DXA for bone mineral density, lean and fat mass		X					X	X
FibroScan for hepatic steatosis and fibrosis assessment		X					X	X
HIV-1 RNA	X		X	X	X		X	X
Safety labs**	X	X	X	X			X	X
CD4 + T lymphocyte count		X		X	X		X	X
Fasting lipids, banked serum and plasma samples for insulin and biomarkers		X			X		X	X
Medication dispensation		X	X	X	X	X		

\* Entry, week 24 and week 48 laboratory evaluations are required to be fasting (at least 8 hours)

\*\*Safety labs include: CBC with differential, chemistry panel including liver enzymes (ALT, AST, Alk Phos), total bilirubin and serum creatinine. All safety labs, HIV-1 RNA, and CD4+ T lymphocyte counts will be performed at local certified laboratories.

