### Fasting lipids, glucose, insulin

Fasting total cholesterol, HDL cholesterol, LDL cholesterol (direct), triglycerides and glucose will be performed at entry and weeks 24 and 48 in real time at the local laboratory. Samples for insulin and oxidized LDL measurement will be batched and analyzed at the end of the study.

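### Section 9.6 gives the baseline measurements no role in comparing the arms and names no paired test for change within an arm; the cost is lost precision, not bias

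*Combined protocol and SAP*

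**What the plan says.** Section 9.6 (Analyses) names two tests, Wilcoxon rank-sum for continuous and Pearson chi-square for categorical variables, and states that these "tests will compare continuous and categorical variables, respectively, between and within groups". The only adjusted analysis is in the same section: "regression modeling will be attempted to assess if any observed differences persist after adjustment for confounding factors". No covariate is listed. The section also says "Data will be pooled by arm and stratified by ART" third-drug class.

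The quantity to be compared is worded in two ways. The secondary objectives in 1.3 compare the arms at week 48, for example "To compare bone mineral density by DXA at 48 weeks between TW who switch". Hypothesis 1.1.2 is about change: the switch "will be associated with improvements in circulating inflammatory and metabolic biomarker profiles" and in several other measures. Section 9.6 does not say whether the level or the change is tested.

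A baseline exists for every secondary endpoint in 9.4:

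- DXA and FibroScan: section 3.0 says these "will be performed at weeks 0 and 48".
- Lipids and glucose: section 6.6 says "Fasting total cholesterol, HDL cholesterol, LDL cholesterol (direct), triglycerides and glucose will be performed at entry and weeks 24 and 48".
- Insulin, oxidized LDL and biomarkers: the 6.1 row "Fasting lipids, banked serum and plasma samples for insulin and biomarkers" is marked at baseline, week 24 and week 48; 6.6 adds that oxidized LDL is measured on batched samples.
- AST, ALT and creatinine (for eGFR): part of the safety labs, marked in 6.1 at baseline and week 48.

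**The concern.** **Between arms.** All ten secondary objectives compare the arms, and the sample size allows for about 20 evaluable participants per arm, so precision is scarce. A baseline value that correlates with the week-48 value removes part of the between-person variation at almost no cost. The plan collects these values but gives them no stated role. The regression sentence does not fill the gap: it is conditional, names no covariate, and asks whether differences already seen survive adjustment. A real difference that the unadjusted test misses is not clearly carried forward.

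Leaving level or change open adds a second risk. Change scores may look like the obvious way to use the baseline, but below a correlation of 0.5 they are less precise than the week-48 value alone.

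**Within arms.** The plan does not define a within-group comparison. If it means third-agent classes inside an arm, these are different people and the named tests are suitable. If it means week 0 against week 48 in the same people, the data are paired. Tests for independent samples then do not have their nominal size, and with positive correlation they are too conservative.

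**Working it through.** **Inputs.** From 9.1: CAP SD 53 dB/m, 20 evaluable per arm, 90% power, difference 56 dB/m. From 9.6: two-sided 5%. The week-0 to week-48 correlation (rho) is not in the documents, so 0.3, 0.5, 0.7 and 0.8 are assumed. The 40 dB/m difference and 30 dB/m change used below are illustrations, not protocol figures.

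**1. The plan's own figure.** A two-sample t-test (noncentral t, 38 df) with 20 per arm and SD 53 has 90.2% power at 56 dB/m, and the detectable difference at 90% power is 55.8 dB/m. The stated figure reproduces. It therefore corresponds to an unadjusted comparison using the full cross-sectional SD.

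**2. Detectable CAP difference under three analyses.** The detectable difference scales with the SD of the quantity analysed:

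- Week-48 level: SD = 53 at any rho.
- ANCOVA on baseline: SD = 53 × √(1 − rho²).
- Change score: SD = 53 × √(2(1 − rho)).

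For example, at rho 0.5 the ANCOVA SD is 53 × √0.75 = 45.9, and 55.8 × √0.75 = 48.3 dB/m.

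| rho | Week-48 level | ANCOVA | Change score |
|---|---|---|---|
| 0.3 | 55.8 | 53.2 | 66.0 |
| 0.5 | 55.8 | 48.3 | 55.8 |
| 0.7 | 55.8 | 39.8 | 43.2 |
| 0.8 | 55.8 | 33.5 | 35.3 |

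At rho 0 the ANCOVA figure returns to 55.8, so nothing material is lost. At rho 0.5 the variance factor is 1 − 0.25 = 0.75, so 20 adjusted participants per arm carry the information of 20 / 0.75 ≈ 27 unadjusted.

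**3. Power for a 40 dB/m difference, like for like (t-based).**

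| rho | Week-48 level | ANCOVA | Change score |
|---|---|---|---|
| 0.3 | 64% | 68% | 50% |
| 0.5 | 64% | 77% | 64% |
| 0.7 | 64% | 90% | 85% |
| 0.8 | 64% | 97% | 96% |

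In simulation (20,000 bivariate-normal replicates), the rank-sum test at week 48 has about 62% power and ANCOVA has 67, 75, 90 and 97%. Type I error is 4.7–5.3% for rank-sum at week 48, rank-sum on change and ANCOVA.

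**4. Within an arm, n = 20, if the comparison is week 0 against week 48.** With positive correlation, the difference between the two time points varies less than the unpaired test assumes. For a test of means the true size is about 2(1 − Φ(1.96/√(1 − rho))), which is 1.9% at rho 0.3 and 0.6% at rho 0.5. Simulation of the named tests (10,000 replicates for the rank tests, 20,000 for chi-square) gives:

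| rho | Rank-sum size | Chi-square size (CAP ≥238) | Rank-sum power, 30 dB/m | Signed-rank power, 30 dB/m |
|---|---|---|---|---|
| 0.3 | 1.97% | 2.28% | 35–38% | 52% |
| 0.5 | 0.88% | 1.38% | 35–38% | 64% |
| 0.7 | 0.18% | 0.58% | 35–38% | 86% |
| 0.8 | 0.04% | 0.24% | 35–38% | 96% |

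The 35–38% is the range across all four correlations. The signed-rank test keeps a size of 4.8–5.3% throughout.

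**The case against.** The strongest defence is that nothing here is invalid. The secondary objectives specify week 48, the CAP calculation reproduces as an unadjusted comparison, and the named test fits both. The study is a pilot with analyses declared exploratory, and the primary endpoint is untouched. This stands: the point is efficiency, and no conclusion would be biased.

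The planned regression might include the outcome's baseline among its confounders, and the plan expects a statistician to oversee further analysis planning. That is possible, but the text does not say so. An adjusted check run after differences have been observed is also not the same as an adjusted main analysis.

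The within-group wording may refer to third-agent classes, which the same section uses to stratify. No objective asks for change within an arm, and a conservative test creates no false positives. All of this stands, so the within-arm part is conditional and the smaller of the two. What remains is an undefined phrase that one sentence can settle.

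Finally, the gain depends on an unknown correlation and is worked out for CAP under normality only. At rho 0.3 it is small. Objective 1.3.6 is framed as a frequency, so ANCOVA does not apply to it in that form. These limits are fair, but they do not argue for leaving the baseline out, because adjustment costs almost nothing even at rho 0.

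**Conclusion.** The point holds. Section 9.6 names no baseline-adjusted main comparison and no paired test, although each secondary endpoint has both a baseline and a week-48 value.

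For CAP, adjustment lowers the detectable difference by about 5% at rho 0.3, 13% at 0.5, 29% at 0.7 and 40% at 0.8 (that is, 1 − √(1 − rho²)). These figures rest on assumed correlations, SD 53 at both time points and normality. The size of the gain for the other endpoints will depend on their own correlations.

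If change within an arm is tested as written, the true type I error is well below the stated 5% and power is reduced. Neither part creates bias or extra false positives. The change is worth making before the data are analysed, because it also closes the open choice between level, change and adjusted results.

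**What to change.** In 9.6:

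- For each continuous secondary endpoint, make the main between-arm analysis an ANCOVA of the week-48 value (log scale where skewed) on arm and the endpoint's own baseline. Add third-agent class if it is used to stratify the randomisation. Report the adjusted difference with its 95% confidence interval.
- Keep the unadjusted rank-sum test at week 48 as a sensitivity analysis.
- Define the within-group comparison. If it includes change over time within an arm, name the Wilcoxon signed-rank test for continuous variables, and McNemar's test or its ordinal analogue for categorical ones.
- For objective 1.3.6, the between-arm comparison of frequencies can stay as planned; HOMA-IR, already listed in 9.4, can be analysed as a continuous variable in the ANCOVA.

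The cost is plan wording and standard code, with no new data or participants. The baseline uses one degree of freedom and third-agent class one or more. Two extra degrees of freedom raise the detectable CAP difference by only about 0.1 dB/m.
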